Study objectives	
Primary objectives:
 
• To evaluate the efficacy of vericiguat 10 mg in comparison to placebo on improving physical functioning from baseline to week 24.• To evaluate the efficacy of vericiguat 15 mg in comparison to placebo on improving physical functioning from baseline to week 24.• To evaluate the safety and tolerability of vericiguat. 
Secondary objectives:
 
• To evaluate the efficacy of vericiguat 10 mg in comparison to placebo on improving distance traveled on a 6-minute walk test (6MWT) from baseline to week 24• To evaluate the efficacy of vericiguat 15 mg in comparison to placebo on improving distance traveled on a 6 MWT test from baseline to week 24.• To evaluate the efficacy of vericiguat 10 mg in comparison to placebo in increasing the proportion of patients with Kansas City Cardiomyopathy Questionnaire (KCCQ) physical limitation score (PLS) improvement from baseline by >5 points at 24 weeks and other thresholds (e.g. >3, >7, >10, >15, >20), and the proportions with these improvements in the other KCCQ domains; overall symptom score (OSS), clinical summary score (CSS), total symptom score (TSS) and symptom frequency score (SFS).• To evaluate the efficacy of vericiguat 15 mg in comparison to placebo in increasing the proportion of patients with KCCQ PLS improvement from baseline by >5 points at 24 weeks and other thresholds (e.g. >3, >7, >10, >15, >20), and the proportions with these improvements in the other KCCQ domains OSS, CSS, TSS and SFS.• To evaluate the efficacy of vericiguat 10 mg in comparison to placebo in decreasing the proportion of patients with KCCQ PLS decline from baseline by >5 points at 24 weeks and the proportions with decline in the other KCCQ domains OSS, CSS, TSS and SFS.• To evaluate the efficacy of vericiguat 15 mg in comparison to placebo in decreasing the proportion of patients with KCCQ PLS decline from baseline by >5 points at 24 weeks and the proportions with decline in the other KCCQ domains OSS, CSS, TSS and SFS.

Clinical Study Protocol
No. BAY 1021189 / 19334

22 FEB 2018

Version no. 1.0

Page: 5 of 81

	
Other objectives:
 
• To evaluate the efficacy of vericiguat 15 mg and the efficacy of vericiguat 10 mg in comparison to placebo on improving
◦ Symptom frequency as measured by the KCCQ SFS◦ Other patient-reported outcomes such as the generic health-related quality of life measure EuroQoL five dimensions five levels questionnaire (EQ-5D-5L) and the Fried-based frailty score◦ New York Heart association (NYHA) class◦ Laboratory variables such as N-terminal pro-brain natriuretic peptide (NT-proBNP) from baseline to 24 weeks• To collect and summarize death including cardiovascular death, and CV hospitalizations including heart failure hospitalizations, myocardial infarction and stroke, and outpatient HF events.• To analyze the cumulative distribution function of KCCQ PLS, OSS, CSS, TSS and SFS change from baseline at 24 weeks• To evaluate pharmacokinetics of vericiguat in patients with HFpEF.• To evaluate the concentration-QTc relationship of vericiguat at the 15 mg dose level.• Optional pharmacogenetic research: To explore the relationship between genetic variation and clinical characteristics of patients, independent and dependent of the treatment administered. Variations across the human genome may be analyzed for association with clinical data collected in this study.• To evaluate further biomarkers to investigate the drug (i.e. mode-of-action-related effect and/or safety) and/or the mechanisms of the disease• Optional accelerometry substudy: To collect exploratory data by activity tracking
Test drug	Vericiguat, BAY 1021189
Name of active ingredient	Vericiguat, BAY 1021189
Doses	2.5 mg, 5 mg, 10 mg, 15 mg
Route of administration	Oral
Duration of treatment	24 weeks
Reference drug	Placebo
Name of active ingredient	N/A
Doses	N/A
Route of administration	Oral
Duration of treatment	24 weeks

**Clinical Study Protocol
No. BAY 1021189 / 19334**

22 FEB 2018

Version no. 1.0

Page: 6 of 81

Background treatment	Standard diuretic and comorbidity treatment
Indication	Treatment of chronic heart failure with preserved ejection fraction
Diagnosis and main criteria for inclusion /exclusion	
Male and female patients aged 45 years or older, with chronic HF (NYHA class II or III), preserved left ventricular ejection fraction (LVEF $\geq 45\%$), elevated natriuretic peptides, and previous HF decompensation will be enrolled in this trial.
 
Main inclusion criteria:
 
 • Previous diagnosis of chronic HF • HF decompensation within 6 months prior to randomization, defined as hospitalization for HF or intravenous (IV) diuretic treatment for HF without hospitalization. • N-terminal pro brain natriuretic peptide (NT-proBNP) ≥ 300 or brain natriuretic peptide (BNP) ≥ 100 pg/mL in sinus rhythm, or NT-proBNP ≥ 600 or BNP ≥ 200 pg/mL in atrial fibrillation within 30 days prior to randomization • Diagnostic criteria of HFpEF by echocardiography assessed within 12 months prior to randomization (most recent measurement must be used to determine eligibility with no interim event signaling potential deterioration in ejection fraction) 
 ◦ Left ventricular ejection fraction (LVEF) $\geq 45\%$ and ◦ Structural changes indicated by at least one of the following parameters: 
 ▪ Left ventricle (LV) hypertrophy (any of the following: intraventricular septal or posterior wall thickness ≥ 1.1 cm, and/or LV mass index ≥ 115 g/m² in male and ≥ 95 g/m² in female), or ▪ Left atrium (LA) enlargement (any of the following: left atrial volume (LAV) index ≥ 29 mL/m², or LAV >58 mL in male and >52 mL in female patients, or LA area >20 cm², or LA diameter >40 mm in male and >38 mm in female patients) • NYHA class II or III at randomization 
Main exclusion criteria:
 
 • Clinical instability at randomization, defined by 
 ◦ Any IV treatment within 24h prior to randomization, and/or ◦ SBP ≥ 160 mmHg ◦ SBP <110 mmHg and/or DBP <40 mmHg and/or symptomatic hypotension ◦ Resting heart rate (HR) <50 or ≥ 100 beats per minute (bpm) • Use of IV inotropes at any time between qualifying HF event and

Clinical Study Protocol
No. BAY 1021189 / 19334

22 FEB 2018

Version no. 1.0

Page: 7 of 81

	
randomization
 
• Previous diagnosis of reduced ejection fraction (EF) (EF <40%)• Hypertrophic obstructive cardiomyopathy, acute myocarditis, amyloidosis, sarcoidosis, or pericardial disease• Primary valvular heart disease requiring surgery or intervention, or within 3 months after valvular surgery or intervention, or active endocarditis• Acute coronary syndrome, including unstable angina, Non ST-elevation myocardial infarction or ST-elevation myocardial infarction, or Coronary artery bypass grafting (CABG) within 60 days prior to randomization, or indication for Percutaneous coronary intervention or CABG at the time of randomization• Symptomatic carotid stenosis, or transient ischemic attack or stroke within 60 days prior to randomization• Complex congenital heart disease• Non-cardiac comorbidity (any of the following)
○ Estimated glomerular filtration rate (eGFR) <30 ml/min/1.73 m² calculated by Modification of Diet in Renal Disease formula○ Hepatic insufficiency classified as Child-Pugh B or C○ Morbid obesity with a body mass index >45 kg/m²○ Malignancy or other non-cardiac condition limiting life expectancy to <1 year, per physician judgment○ Requires continuous home oxygen for severe pulmonary disease or has interstitial lung disease○ Patients with allergies, intolerance or hypersensitivity to investigational drug or any of the excipients• Concurrent or anticipated use of nitrates or NO donors, phosphodiesterase type V (PDE5) inhibitors, or a Soluble guanylate cyclase (sGC) stimulator
Study design	Randomized parallel-group, placebo-controlled, double-blind, multi-center trial
Methodology	
Patients will be randomized 1:1:1 within 4 weeks after the Screening Visit to either:
 
• Placebo arm: placebo and sham up-titration at weeks 2, 4, and 6.• 10 mg arm: vericiguat, which will be started at 2.5 mg at randomization and up-titrated to 5 mg at week 2 and to 10 mg at week 4, with sham titration at week 6.• 15 mg arm: vericiguat, which will be started at 2.5 mg at randomization and up-titrated to 5 mg at week 2, to 10 mg at week 4, and to 15 mg at week 6.

Clinical Study Protocol
No. BAY 1021189 / 19334

22 FEB 2018

Version no. 1.0

Page: 8 of 81

	
The first dose of trial treatment will be administered at the trial site at the randomization visit. Subsequent dosing will be performed once daily by the patient at approximately the same time each day. Patients will be instructed to take vericiguat with food. The titration will be based on systolic blood pressure (SBP) measurement prior to intake and safety considerations, at the discretion of the investigator as follows:
 
• Increase dose: if SBP ≥ 100 mmHg and ≤ 20 mmHg decreases from previous visit, and not yet on highest dose (sham titration will occur if dose increase is chosen from 10 mg in the 10 mg arm)• Maintain dose: if SBP between ≥ 90 and < 100 mmHg or SBP ≥ 100 mmHg and > 20 mmHg decreases from previous visit, or if already on highest dose step (after 3 uptitrations)• Decrease the dose: if SBP < 90 mmHg without symptoms of hypotension if on vericiguat at a blinded dose step > 2.5 mg, or temporarily interrupt if on 2.5 mg (starting dose or after down titration from a higher dose)• Interrupt the dose: if SBP < 90 mmHg with symptoms of hypotension. 
Down-titration is possible at any time during the study. In case of temporary discontinuation or dose reduction after the titration period, up-titration is also possible at scheduled visits. If the period between the scheduled visits is more than 17 and less than 11 days, the patient should attend an unscheduled visit.

Type of control	Placebo
Data Monitoring Committee	Yes
Number of patients	Approximately 735 patients are planned to be randomized, 245 patients per arm.
Primary variable	Change in KCCQ PLS from baseline to week 24
Time point/frame of measurement for primary variable	KCCQ PLS will be assessed at baseline, at weeks 2, 6, 12, and 24
Plan for statistical analysis	
The primary endpoint will be change from baseline to week 24 in physical limitations as measured by the KCCQ PLS. The primary analysis of the primary endpoint will be performed using a repeated-measures mixed model (MMRM), including all assessments post baseline, with baseline values, region, heart rhythm, treatment group, study visit, and the interaction between study visit and treatment group as covariates. The analysis will be performed in the Full Analysis Set.
 
The study is powered at 80% for rejecting either of the primary hypotheses (vericiguat 15 mg arm vs. placebo arm and vericiguat 10 mg arm vs. placebo arm), with the assumption of a mean difference from placebo in KCCQ PLS of 5 points for both dose groups and a common SD of 21 points, under two sided alpha level of 0.05.
 
A planned futility analysis will be performed by data monitoring committee (DMC) when 50% of patients complete Visit 7 (week 12) and their KCCQ data become available. An observed treatment effect of 0.6 point will serve as

Clinical Study Protocol
No. BAY 1021189 / 19334

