3.2.1 Dose selection

The starting dose, as well as the dose range in this study, are based on data from the Phase IIb study SOCRATES, as well as on the Phase I program in healthy volunteers.

In SOCRATES-PRESERVED 4 different dose regimens of vericiguat were studied in patients with chronic HFpEF enrolled within 1 month after a qualifying heart failure decompensation event (20). Data from SOCRATES-PRESERVED established 2.5 mg vericiguat as the safe and well tolerated starting dose. Uptitration by two dose doublings with 14 day intervals each to a target dose of 10 mg was tolerated in patients with HFpEF without an increase in adverse events compared to placebo, with low discontinuation rates in all groups, and no changes in blood pressure at 10 mg compared to placebo. Although analyses of the primary efficacy variables in SOCRATES-PRESERVED did not demonstrate changes in NT-proBNP and LAV at 12 weeks in the vericiguat dose groups compared to placebo, patients receiving vericiguat in the 10 mg target dose arm experienced a more pronounced improvement in health related QoL, physical limitations, NYHA class, signs and symptoms of congestion and trends towards improved diastolic function at 12 weeks (20, 22). These data generate the hypothesis that vericiguat improves physical functioning and clinically relevant patient-reported outcomes in patients with HFpEF. In the parallel SOCRATES-REDUCED study (Study 15371) vericiguat treatment of patients with HFrEF in the 10 mg target dose arm was safe and well tolerated, and resulted in a large biological effect on the primary endpoint NT-proBNP when added to standard of care. Based on these data, the currently ongoing VICTORIA trial evaluates the efficacy of vericiguat in comparison to placebo on a background of standard of care in increasing the time to first occurrence of the composite of CV death or HF hospitalization in patients with HFrEF.

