- Optional pharmacogenetic research: To explore the relationship between genetic variation and clinical characteristics of patients, independent and dependent of the treatment administered. Variations across the human genome may be analyzed for association with clinical data collected in this study.
- To evaluate further biomarkers to investigate the drug (i.e. mode-of-action-related effect and / or safety) and / or the mechanisms of the disease
- Optional accelerometry substudy: to collect exploratory data by activity tracking

5. Study design

[figure not shown]
Design overview

This is a randomized parallel-group, placebo-controlled, double-blind, multi-center trial of vericiguat in patients with HFpEF to be conducted in conformance with GCP. Approximately 735 patients will be randomized as described in [Figure 5–1](#) to evaluate the efficacy of vericiguat 10 mg and 15 mg in comparison to placebo on improving physical functioning from baseline to week 24. To reduce heterogeneity in the studied population patients younger than 45 years of age are not eligible. Patients are expected to be on a background treatment for co-morbidities like hypertension (see [Section 8.1](#)), and diuretics in the presence of symptoms due to volume overload.

Screening may be initiated any time after admission of a patient to the hospital for HF, before or after discharge, and up to 6 months after hospitalization for HF. Use of IV diuretic treatment for HF, even without hospitalization, is indicative of HF decompensation and accepted as a qualifying HF event equivalent to hospitalization. The most recent decompensation should be considered for qualifying the patient for the study. In either scenario, HF must be the primary reason for hospitalization or IV diuretic treatment. Patients will be randomized within up to 4 weeks after the screening visit (see [Section 7.3](#)) and within up to 6 months after the onset of the qualifying event of hospitalization for HF or treatment with IV diuretic for HF (see [Figure 5–1](#)), and treated as given in [Sections 7.1](#) and [7.3](#).

Primary endpoint assessment is at week 24. All patients will be followed until study completion to assess for vital status and all study endpoints.

Figure 5–1 Study design

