EF, ejection fraction; FU, follow-up; HF, heart failure; KCCQ, Kansas City Cardiomyopathy Questionnaire; LAE, left atrial enlargement; LVH, left ventricular hypertrophy; NT-proBNP, N-terminal pro-brain natriuretic peptide; NYHA, New York Heart Association; PLS, physical limitation score; V, Visit.

KCCQ as the entire questionnaire is administered, not just the PLS domain.

Primary variable

Change in KCCQ PLS from baseline to week 24.

Justification of the design

The study is designed to evaluate the safety and efficacy of the 10 mg and of the 15 mg dose regimens of vericiguat at 24 weeks in separate parallel arms. Placebo control is used in a parallel comparator arm to control for observer and patient bias, and randomization to control for assignment bias.

Rationale of study endpoints

To demonstrate durability of efficacy in improving physical functioning and to study safety beyond the previously studied time period of 12 weeks in SOCRATES-PRESERVED, longer treatment duration of 24 weeks has been chosen for this study. This endpoint gives a valid and appropriate measure of the limitations in activities of daily living that are impacted by HF symptoms of breathlessness and fatigue, and represent the key burden of patients suffering from HFpEF. In SOCRATES-PRESERVED in the 10 mg arm a constant rise in KCCQ PLS that did not yet reach a maximum by week 12 was observed. This was opposed to a smaller improvement in placebo that reached its peak at 8 weeks and subsequently decreased. Based on the exploratory finding of a clinically meaningful improvement in KCCQ PLS (i.e. an improvement compared to placebo larger than 5 points upon 12 weeks treatment with a 10 mg target dose regimen) consistent with parallel improvements in EQ-5D-5L in SOCRATES-PRESERVED, the change in KCCQ PLS from baseline to week 24 is defined as the primary endpoint in the present study. This endpoint will serve for confirmatory testing of the hypothesis that vericiguat improves KCCQ PLS compared to placebo on top of background standard of care in a durable manner upon 24 weeks of treatment. Notably, the parallel ongoing event-driven HFrEF outcome trial VICTORIA plans median treatment duration of 18 months to add long-term safety and tolerability data of the 10 mg target dose in HFrEF.

End of study

The end of the study as a whole will be reached as soon as the last visit of the last patient has been reached in all centers in all participating countries (EU and non-EU).

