9.4.1 KCCQ

KCCQ, is a widely used 23-item, disease-specific health status measure intended for the assessment of heart failure patients' perspectives of how their disease impacts their lives (24). It is a self-administered PRO instrument and requires, on average, 4–6 minutes to complete. Patients are asked to recall how their heart failure impacted their life over a 2-week recall period. Response options are on a 5- to 7-point Likert-type scale with varying response options depending on the question.

The KCCQ measures the impact of patients' heart failure, or its treatment, on 6 domains; Physical Limitation, Symptom (with subscores for frequency and burden), Quality of Life, Social Limitations, Symptom Stability and Self-Efficacy. Scores are calculated by summing domain responses and then transforming scores to a 0-100 unit scale with higher scores indicating better health status. In addition, the KCCQ includes 2 summary scores, CSS an equally weighted composite of Physical limitation and Total Symptom domain scores, and OSS which additionally combines the social limitation and quality of life domain scores to the CSS (Table 9–2).

Clinical Study Protocol
No. BAY 1021189 / 19334

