#### **4.4.4 Subgroup analyses**

The following subgroups will be considered for descriptive and exploratory analyses. To determine whether the treatment effect is consistent across various subgroups, the estimate of the between-group treatment effect (with a nominal 95% CI) for the primary endpoint will be estimated and plotted within each category of the following classification variables in all subjects:

- Gender: Male, Female
- Region:
  - Americas
  - Europe (incl. Israel and South Africa)
  - Asia/Pacific
- Heart rhythm: Atrial fibrillation (defined as atrial fibrillation or atrial flutter in baseline ECG), Sinus rhythm (defined as no atrial fibrillation and no atrial flutter in baseline ECG)
- Randomization time:
  - Before discharge from HF hospitalization
  - After discharge from HF hospitalization
  - Post IV diuretic treatment without hospitalization
- Time from qualifying event (HF hospitalization or IV diuretic) to randomization: <3 month,  $\geq$ 3 month
- Baseline Body Mass Index (BMI; kg/m^2):  $\leq$ 30,  $>$ 30
- Baseline Estimated Glomerular Filtration Rate (eGFR; mL/min/1.73m^2):  $\leq$ 60,  $>$ 60
- Diabetes: Yes, No

- COPD: Yes, No
- Anemia: Yes, No
- NYHA class: II, III
- Baseline KCCQ-PLS:  $<45$ ,  $45 - <75$ ,  $\geq75$
- Baseline subgroups defined by combined KCCQ-PLS and NYHA class criteria, as follows: KCCQ-PLS  $<65$  and NYHA II; KCCQ-PLS  $<65$  and NYHA III; KCCQ-PLS  $\geq65$  and NYHA II; KCCQ-PLS  $\geq65$  and NYHA III

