#### **6.2.3 Primary efficacy variable**

##### **6.2.3.1 Primary Analysis of the Primary Efficacy Variable**

The primary endpoint will be change in KCCQ PLS from baseline to week 24.

The estimand of interest is the de facto or treatment policy estimand.

Population: Defined through study inclusion/exclusion criteria (see protocol Section 6.1 and 6.2).

Variable: Change from baseline in KCCQ PLS from baseline to Week 24.

Approach of intervention effect: Regardless of stopping study treatment or adherence to study treatment.

Summary measure: Difference of LS means at Week 24.

The primary analysis will be performed on the FAS (KCCQ) (Section 5.1.2). Missing data will be imputed based on a pattern-mixture model with control-based pattern imputation (Appendix 9.1). The main idea of this method was introduced by Little and Yau (1996) [20] and later refined by Ratitch and O'Kelly (2011) [21]. In this control-based pattern imputation, PROC MI is called in such a way that it builds its imputation model only on data from the control arm, while it imputes missing data in both control and experimental treatment arms using a single control-based imputation model. In other words, the methods will be implemented using copy reference approach. For those patients who had died during the study, they will be imputed with the worst case outcome, i.e., a zero score from the time of death onward.

The analysis of each imputed dataset will be performed using mixed-effects model for repeated measures (MMRM), including treatment, region, heart rhythm, study visit as fixed effects, interaction between study visit and treatment group, and adjustment for the baseline PLS values as covariates. The model will assume an unstructured covariance matrix for within-patient variability.

The model statement is:

$$Y_{ijklm} = \mu + \beta x_i + t_k + r_l + h_m + v_j + (tv)_{jk} + \varepsilon_{ij}$$

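### The primary KCCQ PLS model leaves out time from the qualifying HF event to randomization, a baseline value already collected in days; adding it could gain some precision at almost no cost

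*Protocol*

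**What the plan says.** **Model.** The protocol synopsis fits the MMRM "with baseline values, region, heart rhythm, treatment group, study visit, and the interaction between study visit and treatment group as covariates". SAP 6.2.3.1 describes it as "including treatment, region, heart rhythm, study visit as fixed effects, interaction between study visit and treatment group, and adjustment for the baseline PLS values". The model equations in Protocol 10.3.1 and SAP 6.2.3.1, and the PROC MIXED code in the SAP, contain no term for time since the event or for entry setting. Randomization is stratified by region and heart rhythm only (Protocol 7.3, SAP 3). SAP 6.2.4 analyses the 6MWT in the same manner.

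**Entry.** Protocol 5 states: "Screening may be initiated any time after admission of a patient to the hospital for HF, before or after discharge", with a limit of 6 months after the event. The baseline questionnaire asks patients how heart failure affected them "over a 2-week recall period" (Protocol 9.4.1).

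**Use of the variable.** "Time from qualifying event (HF hospitalization or IV diuretic) to randomization" is a subgroup in SAP 4.4.4, split at 3 months. The randomization setting (before discharge, after discharge, or after IV diuretic without hospitalization) is another. SAP 6.1.2 tabulates the time in days as a continuous baseline characteristic. None of the supportive analyses in SAP 6.2.3.2 adjusts for either variable.

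**The concern.** A baseline PLS recorded in hospital or shortly after discharge covers part of the decompensation. One recorded at month 5 covers a more settled period. Two patients with the same baseline score could therefore have different expected changes to week 24. The visit terms absorb the average course and baseline PLS absorbs part of the difference between patients, but any remaining part tied to recency of the event goes into the residual.

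The documents give one hint of recovery. The earlier HFpEF trial, whose patients were "enrolled within 1 month after a qualifying heart failure decompensation event" (Protocol 3.2.1), showed a "smaller improvement in placebo that reached its peak at 8 weeks and subsequently decreased" (Protocol 5, rationale of study endpoints).

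What is at stake is precision in a trial with 65% power for a single dose and no allowance for dropout (Protocol 10.4).

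**Working it through.** **Inputs from the documents (Protocol 10.3.1 and 10.4).** Difference 5 points; SD 21; 245 per arm, 735 in total; two-sided alpha 0.025 per comparison; success if at least one primary hypothesis is rejected. Stated power: 65% single-dose, 80% either-dose.

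**Step 1: reproduce the plan's power.**
- Standard error = 21 × √(2/245) = 1.897.
- Standardized effect = 5/1.897 = 2.635; critical value 2.241.
- Single-dose power = 65.3% (stated 65%).
- Either-dose power, from a bivariate normal with correlation 0.5 because the two comparisons share the placebo arm = 80.6% (stated 80%).

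Both figures reproduce without the extra covariate.

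**Step 2: what the covariate could explain.** The documents give neither the mix of entry times nor any relation between entry time and PLS change. Both are assumed here. Let p be the share recently decompensated (20-50%) and d the difference in week-24 change between them and late entrants at equal baseline PLS (2-12 points).
- Variance explained: R² = p(1 − p)d²/21² = p(1 − p)d²/441.
- Residual SD after adjustment: 21 × √(1 − R²).
- Equivalent extra patients: 735/(1 − R²) − 735.

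| p | d (points) | R² | SD after | Single-dose power | Either-dose power | Equivalent extra patients |
|---|---|---|---|---|---|---|
| none | none | 0 | 21.00 | 65.3% | 80.6% | 0 |
| 20% | 2 | 0.15% | 20.98 | 65.4% | 80.7% | 1 |
| 50% | 3 | 0.5% | 20.95 | 65.6% | 80.8% | 4 |
| 20% | 5 | 0.9% | 20.90 | 65.8% | 81.0% | 7 |
| 50% | 5 | 1.4% | 20.85 | 66.0% | 81.2% | 11 |
| 50% | 10 | 5.7% | 20.40 | 68.2% | 82.9% | 44 |
| 50% | 12 | 8.2% | 20.12 | 69.4% | 83.9% | 65 |

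Example, last row: R² = 0.25 × 144/441 = 0.082; SD = 21 × √0.918 = 20.12.

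**Step 3: is chance imbalance a further cost?** The arms will differ by chance in the share recently decompensated. This moves a dose-placebo difference with SD d × √(2p(1 − p)/245).
- p = 20%, d = 5: 0.18 points. (0.18/1.897)² = 0.9%.
- p = 50%, d = 12: 0.54 points. (0.54/1.897)² = 8.2%.

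These are the R² values of Step 2. The imbalance is the same variance, already inside the standard error, and must not be added to it.

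**The case against.** The strongest case against is that nothing in the plan is wrong. A prognostic covariate left out of a randomized comparison does not bias the estimate or inflate type I error, and the planned power holds without it. That stands in full.

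Two stronger readings are tempting. A reader might infer that a known recovery effect sits in the error term. The documents do not show one. The earlier trial enrolled only within 1 month of the event, so it has no late entrants to compare with; placebo response or regression to the mean would look the same. Its placebo gain also fell after week 8, whereas the endpoint here is at week 24. A reader might also count chance imbalance as a second harm; Step 3 shows that it is the same one.

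Entry rules narrow the contrast as well. Patients start after clinical stabilization (Protocol 7.1), with no IV treatment in the preceding 24 hours, within blood pressure and heart rate limits (6.2), and in NYHA class II or III (6.1). But 24 hours is much shorter than the questionnaire's recall window, so early entry still matters in principle.

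The subgroup estimates and baseline tables would make an imbalance visible, but they do not adjust the primary estimate. Finally, a heavier remedy is hard to justify. Setting and time overlap, since patients randomized before discharge are mostly early entrants, and the imputation model is built on placebo data only, where small categories could be sparse. That limits the fix, not the point.

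**Conclusion.** The point holds as a possible gain in precision, not as an error. The omission is the same in both documents. The plan itself treats the variable as worth examining, and there is a plausible reason why baseline PLS does not fully stand in for it.

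On the assumed ranges the gain in either-dose power runs from about 0.1 to 3.3 percentage points (80.6% to 80.7-83.9%). At a gap of 2-3 points it is negligible; gaps of roughly 10 points are needed for more than 2 percentage points. No figure in the documents says where in the range the truth lies.

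Two limits apply. The calculation uses a two-group split as a stand-in for a continuous time variable. It also treats 21 as the SD left after the existing covariates; the protocol takes 21 from the literature and does not say whether it is adjusted. If it is not, the share of residual variance explained would be somewhat larger.

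**What to change.** In Protocol 10.3.1 and SAP 6.2.3.1, before unblinding, add one baseline covariate to the primary model: time from the qualifying HF event to randomization, for example as log days, with its interaction with visit so that its effect may differ at week 24. Fix the functional form and the handling of day zero in the text. Make the same change in the 6MWT model (SAP 6.2.4).

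Randomization setting can go into a named supportive model in SAP 6.2.3.2. The placebo-only imputation model in SAP Appendix 9.1 need not be expanded: its example code already omits region and heart rhythm, and the protocol expects few missing data (11.4).

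The cost is a few lines of text and code and five parameters (one per post-baseline visit) among about 735 patients. No new data or patients are needed. The stated sample size and power can stay as they are.
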